**Table 2. Study Activities**

Activity	BL/Wk 0 a	Wk 6	Wk 12	Wk 18 (Optional) b	Wk 24	Wk 36	Unscheduled Visit c	Premature Discontinuation	30-Day Follow-Up Visit d
Informed Consent d	X								
Patient's Global Assessment of Disease Activity (PtGA) e	X	X	X		X	X		X	
Patient's Assessment of Pain (VAS) e	X	X	X		X	X		X	
HAQ-DI e	X	X	X		X	X		X	
Work Instability Scale for RA (RA-WIS) e	X	X	X		X	X		X	
FACIT e	X	X	X		X	X		X	
EuroQol-5D (EQ-5D) e	X	X	X		X	X		X	
Medical/Surgical History f	X								
Vital Signs g	X	X	X		X	X	X	X	X
Body Weight	X	X	X		X	X	X	X	X
Physical Examination h	X								
Physician's Global Disease Activity VAS (PhGA)	X	X	X		X	X		X	
Tender Joint Count (TJC) 	X	X	X	X	X	X	X	X	X
Swollen Joint Count (SJC) 	X	X	X	X	X	X	X	X	X
Concomitant Therapy i	X	X	X	X	X	X	X	X	X
Adverse Event Assessment j	X	X	X	X	X	X	X	X	X
Pregnancy Test k	X	X	X		X	X	X	X	X

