**Table 2. Study Activities (Continued)**

Activity	Wk 48	Wk 60	Wk 72	Wk 84	Wk 96	Every 12 Weeks Until Study Completion	Every 48 Weeks Until Study Completion (Wk 132, Wk 180 Wk 228 and Wk 276)	Final Visit	Unscheduled Visit c	Premature Discontinuation	30-Day Follow-Up Visit q
Patient's Global Assessment of Disease Activity (PtGA) e	X	X	X	X	X	X		X		X	
Patient's Assessment of Pain (VAS) e	X	X	X	X	X	X		X		X	
HAQ-DI e	X	X	X	X	X	X		X		X	
Work Instability Scale for RA (RA-WIS) e	X		X		X	X		X		X	
FACIT e	X		X		X	X		X		X	
EuroQol-5D (EQ-5D) e	X		X		X	X		X		X	
Vital Signs g	X	X	X	X	X	X		X	X	X	X
Body Weight	X	X	X	X	X	X		X	X	X	X
Physical Examination h	X				X		X	X			
Physician's Global Disease Activity VAS (PhGA)	X	X	X	X	X	X		X		X	
Tender Joint Count (TJC) 	X	X	X	X	X	X		X	X	X	X
Swollen Joint Count (SJC) 	X	X	X	X	X	X		X	X	X	X
Concomitant Therapy i	X	X	X	X	X	X		X	X	X	X
Adverse Event Assessment j	X	X	X	X	X	X		X	X	X	X
Pregnancy Test k	X	X	X	X	X	X		X	X	X	X
Blood Chemistry l	X	X	X	X	X	X		X	X	X	X

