## **8.1.5 Efficacy Analysis**

### **8.1.5.1 Efficacy Variables**

The efficacy endpoints of this study include the ACR20/50/70 response rates at Weeks 6, 12, 24, 36, 48, 60, 72, 84, 96 and every 24 weeks thereafter until the end of the study.

A subject will be considered an ACR20/50/70 responder if:

1. The counts for both SJC and TJC have reduced from Baseline by 20/50/70% or more; and
2. At least three of the five remaining ACR core set measures show reduction of 20/50/70% or more in baseline assessment:
  - Patient's Assessment of Pain (VAS),

- Patient's Global Assessment of Disease Activity,
- Physician's Global Assessment of Disease Activity,
- Patient's Assessment of Physical Function by Health Assessment Questionnaire – Disability Index (HAQ-DI),
- hsCRP.

Other efficacy endpoints of this study are:

- Individual components of ACR at every scheduled study visit (Weeks 6, 12, 24, 36, 48, 60, 72, 84, 96 and every 24 weeks thereafter until end of the study):
  - TJC
  - SJC
  - Patient's Global Assessment of Disease Activity
  - Physician's Global Assessment of Disease Activity
  - Patient's Assessment of Pain
  - hsCRP
  - Health Assessment Questionnaire Disability Index (HAQ-DI)
- Proportion of subjects achieving low disease activity (LDA) or clinical remission (CR) based on DAS28 [CRP] or CDAI criteria respectively at Weeks 6, 12, 24, 36, 48, 60, 72, 84, 96 and every 24 weeks thereafter until the end of the study.
- Proportion of subjects achieving CR at Weeks 6, 12, 24, 36, 48, 60, 72, 84, 96 and every 24 weeks thereafter until the end of the study.
- Change from Baseline in DAS28 [CRP] at Weeks 6, 12, 24, 36, 48, 72, 96 and every 24 weeks thereafter until the end of the study.
- Change from Baseline in CDAI at Weeks 6, 12, 24, 36, 48, 72, 96 and every 24 weeks thereafter until the end of the study.
- Change from Baseline in Patient Reported Outcomes at Weeks 6, 12, 24, 36, 48, 72, 96 and every 24 weeks thereafter until the end of the study:
  - FACIT – Fatigue Scale,

- Work Instability Scale for RA (RA-WIS),
- EuroQoL-5D (EQ-5D).

The proportion of subjects achieving Low Disease Activity (LDA) or Clinical Remission (CR), and the proportion of subjects achieving CR will be evaluated at Weeks 6, 12, 24, 36, 48, 60, 72, 84, 96 and every 24 weeks thereafter until the end of the study. The criteria will be based on DAS28 [CRP] or CDAI as follows:

	DAS28 [CRP]	CDAI
LDA	$2.6 \leq \text{to} < 3.2$	$2.8 < \text{to} \leq 10$
CR	$< 2.6$	$\leq 2.8$

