### **Electronic Patient Reported Outcomes (ePRO)**

Patient reported data must be completed for each subject enrolled in this study. Some of these data are being collected with an Electronic Patient Reported Outcome (ePRO) tool called Trialmax, provided by the technology vendor CRF Health of Lansdale, PA, USA. The ePRO system is in compliance with Title 21 CFR Part 11. The documentation related to the system validation of the ePRO tool is available through the vendor, CRF Health, while the user acceptance testing of the study-specific ePRO design will be conducted and maintained at AbbVie.

The subject and physician will enter the data on an electronic device; these data will be uploaded to a server. The data on the server will be considered source, maintained and managed by CRF Health.

Internet access to ePRO data will be provided by CRF Health for the duration of the trial. This access will be available to the investigator and delegated personnel. Such access will be removed at the end of the site's participation in the study. Data from the ePRO tool will be archived on appropriate data media (CD-ROM, etc.) and provided to the investigator at that time as a durable record of the site's ePRO data. It will be possible for the investigator to make paper printouts from that media.

The ePRO data will be collected electronically via a tablet device into which the subject and physician will record required information. The electronic device will be programmed to allow data entry for only the visits specified in the protocol and will not allow for patients or physician to complete more than one of the same assessments at any one visit. Data entered on the device will be immediately stored to the device itself and

automatically uploaded to a central server maintained and managed by CRF Health. The investigator and delegated staff will be able to access all uploaded subject data via a password-protected website up until the generation, receipt and confirmation of the study archive.

The following assessments will be completed by the subject or physician in Electronic Patient-Reported Outcome (ePRO) device:

- Physician's Global Assessment of Disease Activity VAS
- Joint Evaluation Worksheet (Tender Joint Count and Swollen Joint Count)
- Patient's Global Assessment of Disease Activity VAS
- Patient's Assessment of Disease Pain VAS
- HAQ-DI Questionnaire
- Work Instability Scale for RA (RA-WIS)
- FACIT – Fatigue Scale
- EuroQol-5D (EQ-5D)

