5.3 Analysis Windows

Definition of OL-Rx Days (Days Relative to the First Dose of Open-Label Study Drug)

For the purpose of defining analysis windows for the open-label study, OL-Rx Days are calculated for each time point relative to the first dose of open-label study drug. They are defined as the number of days between the day of the first dose of open-label study drug and the specific time point. OL-Rx days are negative values when the time point of interest is prior to the first dose day of the open-label study drug, while OL-Rx days are positive values when the time point of interest is on or after the first dose day of open-label study drug. The day of the first dose of open-label study drug is defined as OL-Rx Day 1, while the day immediately prior to the first dose day of open-label study drug is defined as OL-Rx Day –1 (there is no OL-Rx Day 0). OL-Rx days are used to map actual study visits to the protocol specified study visits.

Definition of Analysis Windows

The following rules will be applied to assign actual subject visits to protocol-specified visits. For each protocol-specified study visit, a target study day will be identified to represent the corresponding visit along with a window around the target day. Windows will be selected in a non-overlapping fashion so that a collection date does not fall into multiple visit windows. If a subject has two or more actual visits in one visit window, the visit closest to the target day will be used for analysis. If two visits are equidistant from the target day, then the later visit will be used for analysis.

The visit window and the target OL-Rx day for each protocol-specified visit are displayed in [Table 1](#).

Table 1. Analysis Windows for Efficacy, Laboratory Assessments and Vital Signs

Protocol Specified Visit Week	Lower Bound	Target Day^a	Upper Bound
Baseline	Last non-missing measurement recorded on or before the date of the first dose of study drug in RCT		
6	2	43	64
12	65	85	127
24	128	169	211
36	212	253	295
48	296	337	379
60	380	421	463
72	464	505	547
84	548	589	631
96	632	673	715
108	716	757	799
120	800	841	883
132	884	925	967
144	968	1009	1051
156	1052	1093	1135
168	1136	1177	1219
180	1220	1261	1303
192	1304	1345	1387
204	1388	1429	1471
216	1472	1513	1555
228	1556	1597	1639
240	1640	1681	1723
252	1724	1765	1807
264	1808	1849	1891
276	1892	1933	1975
288	1976	2017	2059
300	2060	2101	2143
312	2144	2185	2227

a. Relative to the day of first dose of open-label study drug.

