9.1.1 Definition of Missing Data Imputation

As Observed (AO)

The AO analysis will not impute values for missing evaluations. All observed data will be used in the analysis. The AO analysis will be applied to long-term efficacy analysis.

Mixed Model Repeated Measures (MMRM) and Generalized Linear Mixed Model (GLMM)

The repeated measure analysis will be conducted using mixed model including As Observed measurements at all visits. MMRM will be used for continuous endpoints and GLMM will be used for binary endpoints. The mixed models will include the categorical fixed effects of treatment, visit and treatment-by-visit interaction. Prior RCT study will also be included as a fixed factor in the model. For the MMRM analysis of change from baseline in continuous endpoints, the baseline measurement will be included as a continuous fixed covariate. The categorical fixed effect of subject's discontinuation status may also be included in the model as appropriate. Unstructured, Toeplitz, compound symmetry, or other covariance structures may be considered.

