9.2 Long-Term Efficacy Analysis

Assessments to evaluate long-term efficacy will be analyzed for the following measures at Weeks 6, 12, 24, 36, 48, 60, 72, 84, 96 and every 12 weeks until Week 312.

- ACR20/50/70 response rates;
- Change from baseline in individual ACR components;
- Change from baseline in DAS28 (CRP);
- Change from baseline in CDAI and SDAI;
- Proportion of subjects achieving LDA and proportion of subjects achieving CR based on DAS28 (CRP), CDAI and SDAI criteria;
- Change from baseline in Patient Reported Outcomes, including FACIT-Fatigue Scale, RA-WIS, and EQ-5D;

Analyses will be based on As Observed (AO) data. Descriptive statistics will be provided for each treatment group sequence in the Open-Label Treated Population as defined in Section 9.1. These include the number of observations, mean, standard deviation, and 95% CI for continuous endpoints; and frequencies and percentages with 95% CI using normal approximation for binary endpoints. In addition, longitudinal analysis will be

performed using MMRM or GLMM as described in Section 9.1.1 for all endpoints for treatment sequences 1 and 2. Point estimates and 95% CI from the model will be provided. Plots over time will be provided.

Table 1 below provides the overview of the long-term efficacy analysis to be performed on different endpoints.

Table 2. Summary of Long-Term Efficacy Analysis

Measure of Interest	Analysis Method
Binary endpoints: 
 • ACR20 at each visit • ACR50 at each visit • ACR70 at each visit • LDA based on DAS28 (CRP) at each visit • LDA based on CDAI and SDAI at each visit • CR based on DAS28 (CRP) at each visit • CR based on CDAI and SDAI at each visit 	
 • Point estimate and 95% CI of the response rate for each treatment sequence • Point estimate and 95% CI of the response rate using GLMM model for treatment sequences 1 and 2 • Plots over time (for ACR responses and LDA/CR based on DAS28 and CDAI) • Imputation: AO • Population: open-label treated population

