Continuous endpoints: 
 • Change from baseline for DAS28 (CRP) at each visit • Change from baseline for CDAI and SDAI at each visit • Change from baseline for each ACR individual component (i.e., TJC, SJC, Physician's Global Assessment of Disease Activity, Patient's Global Assessment of Disease Activity, Patient's Assessment of Pain, HAQ-DI, hsCRP) at each visit • Change from baseline for other PROs (FACIT, RA-WIS, EQ-5D) at each visit 	
 • Point estimate and 95% CI of mean change from baseline for each treatment sequence together with SD • Point estimate and 95% CI of change from baseline using MMRM model for treatment sequences 1 and 2 • Plots over time (for DAS28 (CRP), CDAI and SDAI) • Imputation: AO • Population: open-label treated population

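### The SAP analyses FACIT, RA-WIS and EQ-5D at Weeks 60 and 84, when they are not collected, and lets off-drug 30-Day Follow-Up values fill efficacy windows

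*SAP*

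**What the plan says.** **Questionnaires.** SAP 9.2 opens with one visit list for all measures: "Assessments to evaluate long-term efficacy will be analyzed for the following measures at Weeks 6, 12, 24, 36, 48, 60, 72, 84, 96", continuing every 12 weeks to Week 312. SAP Table 2 repeats this as "Change from baseline for other PROs (FACIT, RA-WIS, EQ-5D) at each visit", with observed-data summaries by titration sequence and MMRM estimates for sequences 1 and 2. The protocol plans otherwise. Section 8.1.5.1 has "Change from Baseline in Patient Reported Outcomes at Weeks 6, 12, 24, 36, 48, 72, 96 and every 24 weeks thereafter", and section 5.3.3 agrees. In Protocol Table 2 the FACIT, RA-WIS and EQ-5D rows are blank at Weeks 60 and 84, while HAQ-DI, pain and patient global are marked there. All three questionnaires are marked at the Premature Discontinuation visit. Protocol section 10.2 adds: "The electronic device will be programmed to allow data entry for only the visits specified in the protocol".

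**Follow-up values.** Protocol Table 2 marks TJC, SJC and hsCRP at the 30-Day Follow-Up, which section 5.1 places about 30 days after the last dose. SAP 5.3 assigns actual visits to windows that adjoin without gaps. When a window holds several visits, "the visit closest to the target day will be used for analysis", and the later one wins a tie. SAP 9.1.1 uses all observed efficacy data. SAP 10.1 limits safety reporting to the open-label treatment period, but efficacy has no matching limit.

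**The concern.** The two defects are independent of each other.

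First, the Week 60 and 84 questionnaire results would describe people on their way out of the study. The printed N would be small, but nothing would tell the reader that it consists of leavers. The MMRM does not repair this. Each visit has its own mean, and at these two visits the model would have to assume that leavers' scores, given their history, also represent those who stayed. SAP 9.1.1 also says "Unstructured, Toeplitz, compound symmetry, or other covariance structures may be considered". With an unstructured matrix, part of the covariance would have no data behind it.

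Second, some joint counts, hsCRP values and ACR classifications presented as long-term efficacy would be measured about a month after treatment ended. For ACR the error runs one way. A follow-up record holds only one of the five other core measures, so under the examples in SAP 9.4.1 it can be classed as a non-response or as missing, never as a response. If a discontinuation visit shares the window, DAS28, CDAI and SDAI could combine its global scores with off-drug joint counts or hsCRP. Efficacy is part of the study's primary objective, so these summaries are main output even though nothing is tested.

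**Working it through.** **Windows.** All 27 target days in SAP Table 1 equal 7 × week + 1, and the windows adjoin. Week 60 is Days 380–463 (target 421). Week 84 is Days 548–631 (target 589).

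**Can scheduled questionnaires reach those windows?** With the protocol's ±7 days, Week 48 falls on Days 330–344, Week 72 on Days 498–512 and Week 96 on Days 666–680. All lie in their own windows. That leaves Premature Discontinuation visits and grossly mistimed scheduled visits.

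**How many leavers?** The documents give no dropout rate, so I assume a constant yearly rate r. With 494 enrolled, the share still on study at day d is S(d) = (1 − r)^(d/365.25), and leavers in a window number 494 × [S(lower) − S(upper + 1)].

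| r per year | Week 60 leavers | On study at Day 421 | Week 84 leavers | On study at Day 589 |
|---|---|---|---|---|
| 5% | 5.5 | 466 | 5.4 | 455 |
| 10% | 10.6 | 437 | 10.1 | 417 |
| 20% | 19.6 | 382 | 17.7 | 345 |
| 30% | 26.8 | 327 | 22.8 | 278 |

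These counts are then split over three sequences. At equal SD, the confidence interval compared with one from everybody on study is wider by √(on study / leavers): √(466/5.5) ≈ 9.2 at 5% a year and √(327/26.8) ≈ 3.5 at 30%.

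**Covariance.** Twenty-seven visits give 27 × 28 / 2 = 378 elements. A leaver measured in the Week 60 window has no later visit, and 21 visits follow. Nineteen follow Week 84. So 21 + 19 = 40 elements have no subject contributing both values.

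**Which follow-up values are selected?** I took follow-up at last dose + 30 days, the stop at the visit day ± 7, and the discontinuation visit 0–14 days after the last dose (the protocol prefers it within 2 weeks).

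- Stop at Week 18 (nominal Day 127): the last dose is on Days 120–134 and follow-up on Days 150–164, inside the Week 24 window (128–211, target 169) and 5–19 days from target. The discontinuation visit is no later than Day 148, at least 21 days from target. Follow-up is selected in 100%, and still in 100% if follow-up is at 23–37 days.
- Stop at Week 6: follow-up is on Days 66–80, alone in the Week 12 window (65–127). Selected in 100%, or about 91% with follow-up at 23–37 days.
- Stop at an on-time 12-weekly visit (Weeks 12, 24, 36 and 60 checked): follow-up is 23–37 days from target and the discontinuation visit at most 21. Selected in 0%, or 1.3% with follow-up at 23–37 days.
- Last doses evenly spread over Days 85–2154: selected in 68.1%, 65.7% and 63.7% when the discontinuation-visit lag is spread evenly up to 0, 7 or 14 days. With fixed lags of 0, 7 and 14 days the figures are 68%, 63% and 60%.
- On-time completers: the final visit is on Days 2178–2192 and follow-up on Days 2208–2222, which is 23–37 days from the Week 312 target against at most 7. They are not affected.

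The percentages refer to component values at follow-ups where joints and hsCRP were actually measured.

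**The case against.** **Questionnaires.** The confidence-interval comparison uses a data set the protocol never meant to collect, so it shows how thin the results are and does not measure lost precision. That stands. The 40 empty covariance elements matter only if an unstructured matrix is chosen. SAP 9.1.1 allows simpler structures and a discontinuation-status effect. That also stands, but a simpler matrix would still give a Week 60 and Week 84 mean estimated from leavers. The windows can catch a Week 48 visit more than 42 days late, and the documents do not say how often that happens. Last, removing these weeks discards the exit scores of subjects who leave on those days, which models assuming data missing at random would normally use. This is a real cost but a small one. Each visit has its own mean, so values seen only in leavers mostly set that mean and add little to the estimates at other visits.

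**Follow-up values.** Selection of a component is not the same as replacing an ACR result. SAP 9.4.1 takes the nearest non-missing composite, so a follow-up record overrides a discontinuation-visit ACR score only when its joint counts fail. The Week 18 route is narrow, because that visit exists for subjects already failing at Week 12. Later efficacy discontinuations occur at scheduled visits, where selection is 0%. Follow-up may be by telephone, which yields no joint counts, and the protocol says laboratory tests may not be required. The mixing of DAS28, CDAI and SDAI depends on reading SAP 5.3 component by component. Read visit by visit, the score would be missing. Discontinuation visits can also be off drug, with an effective half-life of about 3 hours, so excluding only the follow-up visit is partly a choice of estimand. All of this limits how many results are affected. None of it supplies the missing rule.

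**Conclusion.** Both points hold. The schedule mismatch is certain from the text. SAP version 3.0 aligned its visit list with data collection only after Week 96 and left Weeks 60 and 84 unreconciled. Each of those questionnaire results would rest on roughly 5–27 leaving subjects under assumed dropout of 5–30% a year with scheduled visits on time.

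The missing last-dose limit is equally clear, but its reach is not. The selection rates are 100% for Week 18 stops, 0% for on-time 12-weekly stops and about 60–68% for evenly spread stops. They assume an on-site follow-up near 30 days. The documents give no count of discontinuations or on-site follow-ups, so the number of subjects affected cannot be computed. The plan should be corrected on both points. No hypothesis test depends on either.

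**What to change.** 1. In SAP 9.2 and SAP Table 2, remove Weeks 60 and 84 for FACIT, RA-WIS and EQ-5D only. Leave the Table 1 windows and all other measures unchanged. The 12-weekly schedule after Week 96 matches collection and can stay, which leaves 25 of the 27 visits.
2. In SAP 5.3, add: 'Records from the 30-Day Follow-Up visit after the final dose of open-label study drug are not mapped to efficacy analysis windows. Premature Discontinuation visits and scheduled visits during a temporary interruption remain eligible.'

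The cost is two SAP sentences and a programming filter. Questionnaire scores from discontinuation visits on Days 380–463 and 548–631 leave the visit summaries and the MMRM, and can be listed instead. A few off-drug joint counts and hsCRP values drop out of efficacy. No on-time scheduled questionnaire record is lost.

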9.0 Efficacy Analysis

9.1 General Considerations

Long-term efficacy analysis will be performed on the Open-Label Treated Population by the treatment group sequences as defined below:

1. Upadacitinib never titrated (6 mg BID/15 mg QD),
2. Upadacitinib titrated up and not down (6 mg BID/15 mg QD to 12 mg BID/30 mg QD), and
3. Upadacitinib titrated up and down (6 mg BID/15 mg QD to 12 mg BID/30 mg QD and then back down to 6 mg BID/15 mg QD).

No statistical tests will be conducted; only descriptive statistics and confidence intervals will be provided. All data will be summarized based on As Observed data (defined in Section 9.1.1).

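### SAP 9.2 sets normal-approximation 95% intervals for every binary efficacy endpoint, with no exception for small cells or rates near 0% or 100%

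*SAP*

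**What the plan says.** SAP 9.2 summarises each treatment group sequence in the Open-Label Treated Population with "frequencies and percentages with 95% CI using normal approximation for binary endpoints". Table 2 lists nine binary endpoints: ACR20, ACR50 and ACR70, and low disease activity and clinical remission, each by DAS28 (CRP), CDAI and SDAI. The visits are Weeks 6, 12 and 24, then every 12 weeks to Week 312.

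SAP 9.1 defines three sequences by titration history; the third is "Upadacitinib titrated up and down". The same section says: "No statistical tests will be conducted; only descriptive statistics and confidence intervals will be provided".

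A longitudinal analysis is "performed using MMRM or GLMM as described in Section 9.1.1 for all endpoints for treatment sequences 1 and 2", and it also yields point estimates with 95% intervals. Sequence 3 is not included.

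The missing-data rule in SAP 9.1.1 is As Observed: "The AO analysis will not impute values for missing evaluations. All observed data will be used in the analysis". Protocol 8.1.5.2 asks for 95% intervals without naming a method. Neither document gives a rule for small cells or for rates close to 0% or 100%.

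**The concern.** The Wald interval is known to fail when the cell is small or the rate is close to a boundary. It then covers the true rate less often than stated, can extend below 0% or above 100%, and has zero width when every subject or no subject responds.

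Such cells are plausible here, although the documents do not establish them. Sequence 3 needs both an increase and a later decrease in dose, and follow-up runs to Week 312. High ACR20 rates are plausible among those retained, because Protocol 5.1 withdraws subjects who fail a 20% joint-count improvement and ACR20 requires that same improvement. Low remission rates are plausible in sequences 2 and 3, whose members were up-titrated after missing the joint criterion or CDAI low disease activity.

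With no tests planned, the intervals are how the report conveys precision. At stake is whether a reader sees a falsely tight, zero-width or impossible interval, most of all in sequence 3, where no other interval is offered.

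**Working it through.** **Inputs from the documents.** Nine binary endpoints (Table 2), 27 visits (3 + (312 − 24)/12 = 27) and three sequences (SAP 9.1) give 9 × 27 × 3 = 729 Wald intervals. Of these, 9 × 27 = 243 belong to sequence 3 and have no model-based companion. Enrolment is 494 (SAP 4.2). Sizes by sequence and visit, and expected rates, are not given.

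**The plan's own figure.** SAP 9.2 states no interval width to reproduce. The only precision statement is in the vaccine sub-study (Protocol Appendix O; sub-study SAP 2.4): n = 100, rate 60%, margin about 10%. The Wald formula gives 1.96 × √(0.6 × 0.4/100) = 9.6 points, which agrees. That is a mid-range rate in a fairly large cell.

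**Formulas.** With x responders among n, p = x/n and z = 1.96:
- Wald: p ± z√(p(1 − p)/n)
- Wilson: [p + z²/(2n) ± z√(p(1 − p)/n + z²/(4n²))] / (1 + z²/n)
- Exact coverage at true rate π: the sum of binomial probabilities over all x whose interval contains π.

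**Single tables (assumed counts).**

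| Observed | Wald | Wilson |
|---|---|---|
| 20/20 | 100% to 100% | 83.9% to 100% |
| 0/30 | 0% to 0% | 0% to 11.4% |
| 28/30 | 84.4% to 102.3% | 78.7% to 98.2% |

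For 28/30, p = 0.933, the standard error is √(0.933 × 0.067/30) = 0.0455 and 1.96 × 0.0455 = 0.089. In general a Wald bound leaves 0% to 100% when the observed rate is within z²/(n + z²) of a boundary without reaching it: 16.1 points at n = 20, 11.4 at n = 30 and 3.7 at n = 100.

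**One coverage figure by hand.** Take n = 20 and true rate 95%. The outcome 20/20 has probability 0.95²⁰ = 0.358, and its zero-width interval at 100% misses 95%. At 15/20 the upper Wald bound is 94%, so outcomes of 15 or fewer also miss; together they have probability 0.003. Coverage is 1 − 0.358 − 0.003 = 0.639.

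**Exact coverage of nominal 95% intervals (assumed n and rate).**

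| n | True rate | Wald | Wilson | Clopper-Pearson |
|---|---|---|---|---|
| 20 | 95% | 63.9% | 92.5% | 98.4% |
| 30 | 95% | 78.2% | 93.9% | 98.4% |
| 30 | 90% | 80.9% | 97.4% | 99.2% |
| 50 | 95% | 92.0% | 96.2% | 98.8% |
| 100 | 90% | 93.2% | 93.6% | 95.6% |
| 100 | 95% | 87.7% | 96.6% | 98.3% |

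The same values hold at the mirror-image low rates (5% for 95%, 10% for 90%). Averaged over true rates of 5% to 95%, Wald coverage is about 90% at n = 20, 92% at n = 30, 94% at n = 100 and at n = 200, and 95% at n = 494. The failure is therefore specific to small or extreme cells, and it is uneven: n = 50 does better than n = 100 at a true rate of 95%.

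**The case against.** **Small cells are assumed.** This stands as a limit on size. The sub-study, drawn from the same extension, planned for about 150 subjects, about 100 of them on 15 mg QD. Those are plans and do not map onto sequences, but they do not suggest late cells of 20 or 30 in sequence 1. The option from Amendment 5 to reduce from 30 mg QD to 15 mg QD at the investigator's discretion could also enlarge sequence 3. In large mid-range cells Wald is nearly adequate. None of this supplies a rule for the cells where it is not.

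**The Wald intervals do not stand alone everywhere.** A reader of the no-tests statement might infer that they are the only expression of uncertainty. SAP 9.2 and Table 2 add model-based intervals for sequences 1 and 2, so that reading holds for sequence 3 only. Nor does the open choice in SAP 9.1.1 ("Unstructured, Toeplitz, compound symmetry, or other covariance structures may be considered") make the model intervals unusable: the section names the fixed effects, and Table 2 states the output as a response rate with its interval.

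**The population label.** A reader might infer that Table 2 misdescribes the denominator, since it says "Population: open-label treated population" while a rate at a visit covers only subjects observed then. The same table cell also states the As Observed rule, and Protocol 8.1.5.2 says that unevaluated subjects are excluded from that visit. The denominator is specified. What remains is presentation: SAP 9.2 lists a count explicitly for continuous endpoints ("These include the number of observations, mean, standard deviation, and 95% CI for continuous endpoints") and not for binary ones.

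**Selection.** A reader might go on to infer that As Observed ACR20 overstates response by some stated amount, because the withdrawal rule and ACR20 share the joint criterion. The documents support no figure. Any figure would need invented response and withdrawal rates, and the comparison would be with response had everyone continued, which the SAP does not claim to estimate.

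**Conclusion.** The point holds as a minor one. The SAP fixes the Wald interval for all 729 binary summaries without exception, and for the 243 in sequence 3 it offers nothing else. If a cell has about 20 to 30 subjects and a true rate of 90% to 95% (or 5% to 10%), a nominal 95% interval covers 64% to 81% of the time; at 100 subjects and a rate of 95% it covers 88%. If cells are large and rates moderate, the loss is about a percentage point or less on average. Which case applies depends on cell sizes and rates that the documents do not give.

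No test, error rate, sample size or point estimate is affected. The defect lies in the stated precision only.

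**What to change.** In SAP 9.2, replace the normal approximation with Wilson 95% intervals for binary endpoints, or Clopper-Pearson if guaranteed coverage is preferred. One method for all cells avoids a threshold rule and hardly changes the large ones: at n = 100 and a rate of 50%, mean width is 19.1 points with Wilson against 19.5 with Wald.

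The cost is a line of SAP wording and a different interval option in the software. Intervals become asymmetric, and wider in small or extreme cells: at n = 30 and a true rate of 95%, mean width is 17.3 points with Wilson against 13.2 with Wald. Clopper-Pearson is conservative, with 96% to 99% coverage in the six cells tabulated above.

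As an optional aid to the reader, print the number observed at each visit beside the As Observed rates. This adds one count per cell.
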